5.3 Data synthesis

Findings from WPs1-4 will be synthesised in WP5 to generate overall conclusions about the impact of the SDIL at different time points in its evolution and implementation. We will draw on quantitative (e.g. modelling relationships between observed time trends) and qualitative

techniques (e.g. pattern matching) to enhance causal inference, and generate overall conclusions with stakeholder input.

6 Objectives

We propose an evaluation of the SDIL using a systems approach to enable the wide range of possible impacts of the SDIL, identified and prioritised by stakeholders from our systems map (Appendix A), to be measured and their relationships explored. NIHR is interested primarily in health impacts, but these may be influenced by many other proximal, intermediate and distal impacts, which are likely to interact dynamically. These impacts could be considered simplistically, according to a relatively linear theory of change, but because of the likely existence of feedback loops and unpredictable actions and reactions, representing them in this way is potentially unhelpful. The evaluation will therefore be divided into a series of work packages, each focusing on a set of impacts that are related and for which the research methods are similar, in order to generate a range of evidence that can be triangulated and synthesised. We will primarily use routine data to allow retrospective data acquisition and an efficient design, focusing on the whole of the UK where feasible. All outcomes will be assessed comparatively across the three two-year time periods related to hypothesised intervention points where impacts are likely to be observed:

- *Time period 1:* Prior to the announcement of the SDIL (from April 2014 to March 2016)
- *Time period 2:* following the chancellor's announcement of the SDIL in March 2016 up to confirmation of legislation for the SDIL (anticipated April 2017), and following the confirmation of SDIL legislation (anticipated April 2017) up to implementation of the SDIL (anticipated April 2018)
- *Time period 3:* following implementation of the SDIL (anticipated April 2018) up to 24 months later

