Public discourse surrounding the SDIL will be similarly tracked in three ways:

- *News media coverage* will be identified by interrogating the LexisNexis database using a pre-determined search strategy that will be refined following initial scoping, to identify all articles referring to regulation of sugar in food/drinks, or to the SDIL specifically in national newspapers and trade (food industry) press from 2 years before announcement of the levy until 2 years after implementation. It is likely that articles will be clustered sporadically. Searches and screening of articles will therefore take place at the end of time periods 2-3. Depending on the volume of material, we may need to sample articles from each time period to limit workload, while achieving thematic saturation. The majority of national press articles can be accessed online, where public reactions to articles can also be found. This public discourse will also be sampled and analysed iteratively, to saturation.
- *Social media discourse* will be identified via analysis of Tweets, which will be collected using both specific keywords and also by following Twitter accounts of key individuals and bodies, from October 2016 until March 2020. This will include data on public and professional (e.g. public health, industry) discourse, as well as advocacy from civil society organisations and individuals, which will be triangulated with other sources (see below). Relevant tweets from each of the four time periods will be identified using search strategies (determined during our current formative work) to identify discourse on the SDIL. Key sources (twitter accounts) identified as commenting on the SDIL in early searches will be routinely searched in subsequent searches for continuing discourse (e.g. Faculty of Public Health, British Soft Drinks Association, Jamie Oliver). The volume of material is likely to be high. For qualitative analysis, to ensure a manageable quantity of data, we will prioritise 'popular' tweets (e.g. highly retweeted) and those from key stakeholders, as well as sample material for content analysis, which will continue to saturation. We will also undertake network analysis to explore the spread of discourses between groups and over time. Detailed methods are being developed in our formative work.

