- Documentary sources, including news and social media content: Data from documentary sources will be analysed qualitatively using thematic content or critical discourse analysis, as appropriate, assisted by NVivo software. Rather than a static analysis at a single point in time, sequential analyses will be undertaken using data from key time segments corresponding to the phases of the introduction of the SDIL (i.e. mirroring the quantitative analyses). Using this approach we will be able to explore how prevailing narratives for each group of interest (public, professional, industry, political) develop over time as plans for the SDIL develop and solidify. A dialogue between the qualitative and quantitative analyses will allow us to explore the extent to which the development of narratives appear to be contingent on the emerging processes and outcomes of the SDIL. This approach will be strengthened by longitudinal analysis of data from key sources with ongoing⁸⁰ discourse on the SDIL (e.g. specific newspapers, trade journals or twitter accounts). We will also use network⁸¹ and sentiment analysis⁸² of the accumulated relevant tweets to identify the trends, spread and emergence of discourses, and relationships between key stakeholder discourses.
- Interview and focus group data: Data from face to face dialogues will be analysed thematically,⁸⁰ assisted by NVivo/Atlas.ti software, using the Framework method⁸³ with constant comparison⁸⁴ and deviant case analysis⁸⁵ to enhance validity. Initial frameworks will be developed from interview topic guides and modified iteratively using emergent themes, so that earlier transcripts influence the analysis of subsequent transcripts. As with the analysis of documents, interviews and focus groups will be analysed in time segments corresponding to the implementation phases of the SDIL. The enquiry will be strengthened by longitudinal analysis of data from focus group panels allowing investigation of emerging discourse on the SDIL.

All data will be anonymised following transcription to preserve the anonymity of individual participants or organisations where possible. A sample of all qualitative data will be independently analysed by a second researcher to ensure reliability of the thematic coding frameworks. Data clinics involving WP4 team members will also be held to achieve consensus in data interpretation. Any data that are unavoidably identifiable will only be used with the consent of the relevant participants.

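### Tweets are collected only from October 2016 although every time period is to be covered, and carrying accounts forward lets capture differ between phases

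*Protocol*

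**What the plan says.** Section 6 (Objectives) sets the frame for the whole evaluation: "All outcomes will be assessed comparatively across the three two-year time periods". Period 1 is "Prior to the announcement of the SDIL (from April 2014 to March 2016"). Period 2 opens "following the chancellor's announcement of the SDIL in March 2016 up to confirmation of legislation for the SDIL (anticipated April 2017") and then runs on to implementation, anticipated for April 2018. Period 3 is the 24 months after that.

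In Section 7.4, social media discourse is captured by keyword and "by following Twitter accounts of key individuals and bodies, from October 2016 until March 2020". The same paragraph says "Relevant tweets from each of the four time periods will be identified using search strategies", and adds a carry-forward rule: "Key sources (twitter accounts) identified as commenting on the SDIL in early searches will be routinely searched in subsequent searches". The focus-group paragraph of that section schedules groups in periods 2 to 4.

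Under Data analysis in Section 7.4, documentary sources, including social media, are analysed in segments matching the SDIL phases, in parallel with the quantitative work. Network and sentiment analysis of the accumulated tweets is then meant to "identify the trends, spread and emergence of discourses, and relationships between key stakeholder discourses".

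**The concern.** There are two separate problems.

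**Coverage.** The paragraph promises tweets from periods that its own collection window does not reach. Anyone relying on it would expect a Twitter baseline before the announcement, and there is none.

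**Comparability within the window.** An account that enters through the carry-forward rule is searched directly in later rounds. In the first round its tweets were found only if they matched the keywords. The same underlying activity can then yield more captured tweets later than earlier. Following sources forward suits qualitative tracking of a continuing conversation. It becomes a difficulty when the same corpus is used for trends and networks, because a change in discourse and a change in capture cannot be told apart.

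WP4 findings go into the WP5 synthesis, where agreement between sources is used to strengthen causal inference. An artefact of capture could be read there as corroboration.

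**Working it through.** **1. Coverage.** The inputs are the tweet window (Section 7.4) and the period dates (Section 6), with period 2 split at the anticipated legislation date of April 2017. October 2016 to March 2020 is 3 + 36 + 3 = 42 months.

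| Segment | Months in segment | Months with tweets | Share |
|---|---|---|---|
| Before announcement, Apr 2014–Mar 2016 | 24 | 0 | 0% |
| Announcement to legislation, Apr 2016–Mar 2017 | 12 | 6 | 50% |
| Legislation to implementation, Apr 2017–Mar 2018 | 12 | 12 | 100% |
| After implementation, Apr 2018–Mar 2020 | 24 | 24 | 100% |
| All | 72 | 42 | 58% |

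The six missing months of the second segment are the first six, so the announcement and the summer 2016 consultation fall outside the window.

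**2. Number of periods.** Section 6 defines three. Splitting period 2 at legislation gives four, which fits the Twitter paragraph and the focus-group numbering, but the first of the four then has no tweets. The four could instead be the announcement, legislation, introduction and post-introduction phases named in Section 7.3. On that reading the announcement phase still lacks the announcement and about six months of reaction.

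**3. Comparison with Study 1a.** Section 7.1 faces the same start date for FoodDB. It says that full data begin six months after the announcement, and it restricts the analysis to one intervention point, implementation. Section 7.4 has no matching restriction for Twitter.

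**4. Direction of the capture effect.** The protocol gives no figures for this step, so every input is an assumption: three phases, constant true activity averaging 2 tweets per account per phase (Poisson), keyword sensitivity *k*, a share *d* of accounts replaced between phases, and full capture of any listed account. An account is listed if the keywords caught at least one of its tweets. The captured share is *k* in phase 1. In phase 2:

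- listed share L = (1 − d)(1 − e^(−2k))
- captured share = L + (1 − L)k

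With k = 0.3 and d = 0.1, L = 0.9 × 0.451 = 0.406, and the captured share is 0.406 + 0.594 × 0.3 = 0.58, against 0.30 in phase 1. New accounts then make up 0.1 × 0.3 / 0.58 = 5% of captured tweets, against a true 10%.

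A simulation over three phases, with d = 0.1 and 0.3, gave:

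| k | Phase 1 share | Phase 3, list extended each time | Phase 3, list frozen after first search |
|---|---|---|---|
| 0.3 | 0.30 | 0.60–0.72 | 0.45–0.55 |
| 0.6 | 0.60 | 0.84–0.92 | 0.74–0.83 |
| 0.9 | 0.90 | 0.96–0.99 | 0.94–0.97 |

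Capture rises in every case. If the list is frozen, it rises once and then slips. New accounts are under-represented at low sensitivity (4–5% against 10%, and 15–20% against about 30%) and close to the truth at k = 0.9 (9% against 10%, and 29% against about 30%).

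**The case against.** The strongest reply has four parts.

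- **The announcement is covered by other sources.** News media are searched from two years before it, the consultation submissions are a key analysis, and the formative work prioritised documents and interviews on immediate reactions. No before/after contrast on tweets alone is planned, and tweets are to be triangulated. This stands: the evaluation as a whole is not blind to the announcement. What remains is that the limit on Twitter is unstated and the wording claims otherwise.
- **Carry-forward is a panel design.** Its stated purpose is to follow continuing discourse from key sources. This stands for the qualitative strand. It does not help trend measures that pool carried-forward and keyword-captured tweets.
- **Keyword capture runs in parallel under pre-specified strategies.** This stands and bounds the effect. With high sensitivity, little distortion is left.
- **Detailed methods are deferred to the formative work.** This stands for harvesting detail. However, the window, the period wording and the carry-forward rule are already fixed in the protocol.

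A reader might also infer that the account list grows at every search, that tweets come only from listed accounts, or that both spread and emergence must rise by construction. The text supports none of these. It speaks of accounts from early searches, it runs keywords alongside, and for new voices the illustration points downward. No numerical growth in accounts can be derived either, because the protocol gives no account counts or number of search rounds.

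**Conclusion.** The coverage point is certain on the stated dates. There are no pre-announcement tweets, half of the announcement-to-legislation year is missing, and the period count conflicts across sections.

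The capture point holds as a risk. As written, the rule allows capture to differ between phases, so apparent changes in volume, spread and sentiment may be partly artefact. Its size is unknown. Under the assumptions above it ranges from a few percentage points of captured share, when keywords find 90% of relevant tweets, to a doubling or more when they find 30% and the list keeps being extended. If the list is settled after the first search, the main jump comes once, between the first and second phases. The illustration covers captured volume and the share of new accounts. That spread and sentiment are also affected is reasoning, not calculation.

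This concerns one source within WP4, with no effect estimate or hypothesis test stated for tweets alone. It does not undermine the study of the announcement through other sources.

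**What to change.** 1. Reconcile the Twitter paragraph with Section 6 and with the focus-group paragraph: use one set of period labels, and state which segments the tweet window reaches.
2. State that Twitter cannot address the pre-announcement period or the announcement, and that the news-media series already planned serves that comparison. This parallels the restriction given for FoodDB in Study 1a.
3. Compute all trend, network and sentiment measures on one constant capture frame for October 2016 to March 2020. This can be keyword-only, or the same keywords plus an account list that is either fixed or searched back to October 2016.
4. Keep tweets captured only through carried-forward accounts for qualitative follow-up.

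The cost is a change of protocol wording and a filter or back-search in the analysis. The drawback is that later-identified accounts that cannot be searched back drop out of the trend measures.

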7.5 WP5 – Integrate, synthesis and dissemination of findings from WP 1-4

We will integrate and synthesise the findings from WPs 1-4 in order to develop a coherent overarching interpretation of the findings. To achieve this, we will first map our findings on to our systems diagram (Appendix A), in order to test and refine our underlying intervention theory for the SDIL. As this is an area without established methods, we will conduct a scoping review to identify a range of evidence integration and synthesis methods, develop criteria to assess their appropriateness for use within the context of synthesising data and evidence available as a result of the SDIL evaluation and select a set of appropriate methods. These methods will not be restricted in terms of their disciplinary origin, and will reflect approaches used within epidemiology, systems science, behavioural and social science. Broadly, this could involve further quantitative analysis to explain outcomes, such as mediational analyses or exploration of the relations between time trends in outcome variables (e.g. using Dynamic Regression or ARIMAX modelling).⁸⁶ Findings generated using different methods (qualitative, quantitative) could be triangulated to explore the extent to which they provide a consistent interpretation and conclusions about the impacts of the SDIL using pattern matching⁸⁷ and causal process

observation,⁸⁸ thus strengthening causal inference.³⁶

To gain further validation of our interpretation, findings will be shared with key stakeholders (professional and public) in engagement workshop events, in which we will seek their detailed reactions and reflections on specific analyses, findings and interpretations. These will be formally documented and contribute to our final interpretation and conclusions.

During WP5, we will seek wide dissemination of our findings by a variety of means, including presentation at national and international conferences and publication in high-impact journals, preparation and dissemination of policy briefings and policy briefing events, and use of social media and web sites.

8 Setting

The focus of the research will be the United Kingdom, all of which is covered by the SDIL. There may be differences in impacts across the country by region, and we will explore whether these might be captured using routine data. Where data are not available at UK level, the largest geographical area will be used.

9 Data monitoring, quality control and quality assurance

The MRC Epidemiology Unit, University of Cambridge is the lead institution. Collaborations with LSHTM and University of Oxford will be governed by formal collaboration agreements and financial sub-contracts. The University of Cambridge will act as sponsor.

The PI ([name]) will have primary responsibility for scientific and strategic oversight, supported by work package (WP) leads and co-leads (listed below). A senior post-doctoral researcher will work on WP4 and act as overall project manager, responsible for day-to-day coordination of the Work Packages (WPs), liaising closely with the WP leads and co-leads.

A Programme Management Group comprising the PI and WP leads will meet monthly face-to-face or by teleconference. All investigators and research staff will attend bi-annual investigator meetings. Additional, regular WP meetings will take place as required by the work schedule. Collaborators, stakeholders and PPI representatives will be invited when appropriate to seek their input. An independent Study Steering Committee (Independent chair, 2 independent scientific members, 2 PPI representatives – appointed by NIHR) will meet annually with the Programme Management Group to provide external oversight.

The research will be undertaken to the highest ethical and research governance standards, complying with current guidelines and legislation, including the Research Governance Framework for Health and Social Care and Data Protection Act.

10 Ethics and regulatory issues

This work will comply with the ESRC research ethics framework and follow the guidance of Ethical Research Involving Children (ERIC) where appropriate. A significant part of the work involves the use of existing routine data sources, where ethical approval was sought and managed by data providers (WP1, WP2 & WP3) or not required (WP5). All research involving primary data collection (interviews and focus groups) will be subject to ethical committee approval. We will apply for approval through the Humanities and Social Sciences Research Ethics Committee at the University of Cambridge, which gave approval for our formative research that included an online survey and telephone interviews.

All interview and focus groups will be completed with informed consent, or assent by parents for secondary school children, with the right to withdraw consent at any time, providing all participants with an opportunity to review the risks and benefits prior to participation either in person or via email (as appropriate), with no details withheld. There are minimal ethical risks to participation in this work given that no sensitive personal questions will be asked. However,

stakeholders in different organisations may feel their personal opinions relating to the levy are counter to the interests of their organisation. In order to reduce any risk of feeling conflicted, we will reinforce the desire to share their perspective from an organisational perspective and also that their participation is non-identifiable (interviews only) and non-attributable in research outputs (interviews/focus groups), and that they are able to withdraw at any time. Similarly, the general public may feel sharing preferences for consuming soft drinks is stigmatising. They will be reassured that their participation will be non-identifiable (interviews only), and are free to withdraw at any time. Questions will be developed to minimise this risk and all quotations in research outputs will be completed anonymised.

The MRC Epidemiology Unit has an over-arching data management plan that includes standards and processes applied to all research and operational activities of the Unit. The PI will ensure that all data generated, stored and shared will be handled in compliance with this plan. Research staff are trained in handling qualitative data, and taking the proper steps regarding data security. All data collected through telephone or in personal interviews or focus groups will be link-anonymised with any personally identifiable information and stored separately. All data, where appropriate, will be held on the Unit's secure network.

11 Study reporting and publication

We will seek wide dissemination of our findings by a variety of means, including presentation at national and international conferences and publication in high-impact journals, preparation and dissemination of policy briefings and policy briefing events, and use of social media and web sites.

12 Study timetable and milestones

The overall timeline for work packages will overlap over the duration of the project (Appendix C). In summary, we have proposed the following timetable and milestones:

- WP1 – Initial data acquisition and preparation completed by December 2017 and after levy implementation by December 2020. Initial analysis of outcomes will be completed by December 2018 and after levy implementation by December 2021.
- WP2 – Data audit and acquisition will be completed by June 2021, model preparation by September 2021 and scenario analysis and papers completed by December 2021.
- WP3 – initial data acquisition and preparation for macro-economic modelling will be completed by March 2018 and after levy implementation by June 2020. Initial model construction will be completed by June 2019 and after levy implementation by September 2021, with analysis and papers completed by June 2019 and December 2021 respectively. Micro-economic modelling will be completed by June 2019 and December 2021 respectively.
- WP4 – Ethical approval will be obtained by January 2018. Participant recruitment, interview and focus group data collection, qualitative analysis and papers will be

completed by April 2019 and February 2021, and content and media analysis and papers completed by March 2018, October 2019 and May 2021.

- WP5 – System map revision and synthesis of findings will be completed by September 2021. Final report to NIHR and other outputs (e.g. policy briefings), and stakeholder impact events by December 2021

13 References

4. Sugar Reduction The evidence for action: Public Health England, 2015.
